## **TRIAL MANAGEMENT**

### **List of Participating Enrolling Clinics or Data Collection Centers**

The study will be conducted at the ANTHC in Anchorage and at Mayo Clinic. All data collection and the intervention will be conducted by study staff at ANTHC and Mayo Clinic. Data will be collected and maintained by the Mayo Clinic Survey Research Center via Qualtrics software. ANTHC will collect and maintain data electronically in a secure REDCap database.

### **Projected Timetable**

A 3-year timeline is proposed. The formative work will take place in months 1-20 and recruitment for the pilot trial will occur in months 21-27, with intervention, follow-up and analyses completed by month 33. The remaining months will be spent on dissemination activities.

### **Target Population Distribution**

Nearly all (98%) of participants will be of AN race. All participants will be of legal smoking age, 19 years of age or older. Both males and females will be enrolled. We expect that about half the sample (50%) will be female based on our prior studies.

## **DATA MANAGEMENT AND ANALYSIS**

### **Data Acquisition and Transmission**

All data collected by Mayo Clinic study staff will be done via the Qualtrics website, which is managed by the Mayo Clinic Survey Research Center. Data collected on paper forms by the ANTHC project coordinator will be entered into a secure REDCap database. Confidentiality will be maintained by all data containing only a sequentially assigned study number for each subject. The study number will not be linked to the subject's date of birth, village, hospital or any medical record number, initials, social security number, or any other identifying information. All hard copies of data will be kept in secure locked file drawers. [name], Biostatistician on this protocol, will oversee the transfer of electronic data and data storage. The quality of the data (data checks) will be monitored once per month.

Five years after publication of the results (per many journal guidelines) the paper forms and electronic databases will be destroyed. Only summaries of group data will be reported in any publications or presentations, with no identification of individuals.

Permission to audiotape the qualitative interviews in the first phase of the research will be included in the verbal consent process. Once the interviews are fully transcribed the audiotapes will be destroyed immediately.

All biospecimens for the pilot RCT will be labeled with subject ID number only. Once the result from the laboratory analysis is completed at Mayo Clinic, the biospecimen will be destroyed immediately. Test results will be posted electronically using subject ID number only.

The Mayo Clinic Division of Biostatistics has a well-developed structure for data management with over 7,000 studies currently under their control. Working data is maintained on a single large file server that services the entire section. Inactive files are moved to archival storage under control of an automated system, itself controlled by a DBMS (Ingres) based request system which ensures that all data movement is appropriately logged and commented. The archival storage is hosted on the institutional mainframe computer, which also supports billing and registration. The use of the mainframe ensures several high-level support functions for the archive system, e.g. storage of media in separate fire zones, regular copying of data to new media, guaranteed availability.

The data management will be governed by standard procedures within the division with regard to data security and access. All analyses are logged with respect to IRB authorization, accounting information, principal and secondary investigators, statistician, and data analyst involved in the analyses. All computer files and systems will be password protected and accessible by authorized personnel only.

### **Data Entry Methods**

As the Qualtrics website is being utilized through the Mayo Clinic Survey Research Center to administer consent as well as assessments, most quantitative data will be automatically entered. Any data not automated will be entered by the Anchorage staff using a secure REDCap database. Discrepancies will be corrected by [name], Biostatistician on this protocol. [name] will oversee all data entry. All qualitative data will be transcribed by a professional transcription service and imported into QSR NVivo software, version 10, for analyses.

## **QUALITY ASSURANCE**

A manual of study procedures will be developed for the project coordinator. [name], a Mayo Clinic research assistant, and clinical trials coordinator will travel with [name] to Anchorage, Alaska to train the study staff on the data collection and other study procedures. We will use the same coordination, communication and quality control procedures successfully utilized in our previous work. For ongoing trials in Alaska, we hold weekly conference calls with study staff in AK and at Mayo Clinic to discuss progress and problem solve issues related to recruitment and data collection. We also monitor quality control of the data on site through review of participant forms and procedures every 3 months.

[name], Biostatistician on this protocol, will oversee the transfer of data forms and data storage. The Mayo Survey Research Center will electronically transfer all data to [name]. The quality of the data (data checks) including missing data and presence and frequency of outliers will be monitored once per month by [name]. For study recruitment, [name] will track posting of ads through FB and in Alaska local newsletters and websites.

For qualitative data collection, a semi-structured interviewer guide will be developed and the project coordinator in Alaska will conduct the interviews. [name] and [name] will provide training for the project coordinator on-site in Anchorage including four hours of didactic instruction followed by four practice hours of mock interviews and a certified completion interview (Krueger & Case, 2009). All sessions will be audiotaped.

The moderator for the FB-delivered intervention will report to [name], Alaska site PI and work in tandem with the project coordinator. The moderator will be trained on-site in Alaska by Drs. [name] and [name] using didactics and mock Facebook postings and a “refresher” training will occur 6 months after the initial training. The research team will develop a written guide for how often the moderator should log in and expectations for his/her engagement. A potential concern about using social media for health interventions is that user postings may be of poor quality, for example, inconsistent with clinical practice guidelines or involve inappropriate or illegal activities. When participants enter the study they will be informed about the policies for posting content and that any inappropriate postings will be removed. The moderator will be trained to handle inappropriate or misinformation, and to direct information content toward evidence-based information exchange and social support. A process evaluation checklist will be developed for the moderator to document delivery of specific intervention components based on existing measures. A random sample of 20% of moderator postings and responses to participant inquiries and discussions will be selected every week for the first four weeks and monthly thereafter. These transcripts will be coded by [name] to assess counselor adherence to the proscribed intervention, and feedback will be provided to the moderator during weekly research team teleconferences.

All study staff and volunteers will be required to complete and pass the CITI HIPPA/confidentiality course prior to any subject contact.

## **Regulatory Issues**

### **Reporting of Serious Adverse Events (SAEs)**

Any SAE, whether or not it is related to the study intervention and for all participants, will be reported to the Mayo Clinic and Alaska Area IRBs and NIDA. A summary of the SAEs that occurred in the previous year will be included in the annual progress report to the NIDA.

### **Reporting of IRB Actions to the NIDA**

Any action taken by the respective IRBs regarding SAEs or major changes to the protocol will be reported to the NIDA.

### **Report of Changes or Amendments to the Protocol**

Minor changes to the protocol are allowed without prior approval, however, major design changes will be reviewed and approval sought from the NIDA Program Officer prior to seeking IRB approval and implementation.

### **Trial Stopping Rules**

Specific stopping rules have been developed to protect the safety of our study subjects. In the case of any SAE, the study will be stopped and no further enrollment will take place until an investigation of the event has taken place by the PI ([name]), Alaska site PI ([name]) or the project coordinator.

### **Disclosure of Any Conflict of Interest in the DSM**

There are no conflicts of interest in the DSM plan that we are aware of. If such conflicts arise

during the course of the trial, the respective IRBs and the NIDA will be notified immediately.

## **TRIAL SAFETY**

### **Potential Risks and Benefits for Participants**

Risks are minimal and include those associated with the inconvenience of completing assessment interviews by telephone, of providing saliva samples, and online assessments. A trained research assistant at Mayo Clinic will mail the saliva sample kit to the participant; and providing and mailing the biospecimen back to Mayo Clinic for analysis (no identifiers) should not present a risk to subjects. No medications will be administered as part of this study. Data collected from survey responses will be handled by the Mayo Clinic Survey Research Center which uses Qualtrics data security service and a de-identified data base of responses will be provided to the investigators. Qualtrics meets requirements set by the Federal Information Security Management Act of 2002, the Health Insurance Portability and Accountability Act, and the Health Information Technology for Economic and Clinical Health Act. Qualtrics servers are protected by high-end firewall systems, vulnerability scans are performed regularly, and complete backups of the data are performed nightly. Qualtrics uses Transport Layer Security (TLS) encryption (also known as HTTPS) for all transmitted data. We also protect surveys with passwords and HTTP referrer checking. Survey data is hosted by third party data centers that are SSAE-16 SOC II certified. All data are considered confidential, and treated as such, with no specific designation (such as medical (PHI), PII, or public). Finally, Mayo Clinic uses secure and certified data centers. Some data collected by ANTHC study staff will be entered by ANTHC study staff using a secure REDCap and transferred electronically to Mayo Clinic.

In our moderated Facebook intervention, it is impossible to know in advance what might be posted by users, and it is possible that incorrect postings or postings that might cause some emotional discomfort could occur.

Participants will be encouraged to contact the moderator and/or project coordinator if any issue arises that causes them to feel uncomfortable. There are also some minimal risks with respect to confidentiality. As a member of a secret Facebook group, participants will be asked to talk about his/her own tobacco use and others 'use of tobacco, and participate in discussions about moderated postings regarding AN tobacco use, readiness to quit tobacco, and tobacco treatment resources, among others. Thus, it is possible that health information or other personal information about study participants or other AN members could be disclosed on FB postings. To ameliorate concerns, a list of do's and don'ts for posting on the secret FB page will be posted at the front of the page so that whenever a participant joins the FB group, they will be reminded of these guidelines for sharing information, protecting confidentiality, and posting appropriately. Participants will be asked and encouraged to not mention specific names of people in their house or community. A trained moderator will monitor user postings and guide participants in culturally appropriate postings that do not violate confidentiality or harm FB group members. If someone is offended by FB postings, they can message the moderator to resolve any concerns. Any adverse events related to the FB group will also be reported as described if necessary. Despite these arrangements, we do not anticipate any adverse consequences of participating in the secret FB group. The FB group will be secret and closed so no one will be able to join the group, locate the group through a FB search, or see reactions or postings to the group through FB notification unless they are an official and invited member of the secret and closed group.

Information from the group will not be shared with anyone else except for the research team. The FB group moderator will emphasize confidentiality of the group discussions. Moreover, while data from this study will be published, participants will be informed that their name, village and other identifying information will not be published. No voices or images from the audio tapes or from the focus groups will be released. Permission to audio tape will be part of the verbal consent process. Confidentiality of the audio tapes will be maintained by keeping these in a locked drawer in the study office. Only the research team will review the audio tapes. Once the audio tapes are transcribed, they will be destroyed

immediately. In the formative phase of the research, some participants will be recording their smoking cessation stories for the intervention. These individuals (8-12) will sign a release stating they give permission for the study team to share their stories and they will be made aware that their stories will become a part of the public domain and will be seen by study participants on a secret Facebook page.

For participants who stop using tobacco in the pilot RCT, although uncomfortable, withdrawal symptoms do not pose significant health risks. Smoking cessation can result in increased irritability, depression, anxiety, tension and increased hunger and drowsiness. Participants in both study conditions will receive resources that address potential nicotine withdrawal symptoms and how to manage these. In addition, those who call the Alaska quitline will receive support on their quit attempt by a licensed quitline counselor as well as a bevy of support materials in print and online. All phase 4 subjects will complete online assessments via Qualtrics at baseline, 1, 3 and 6 months completion; and at these times any adverse symptoms will be assessed and those reporting adverse symptoms will be called by study staff and referred for appropriate treatment if necessary.

Screening data will not include any unique identifiers and will be used for descriptive purposes only (i.e., to characterize the population of individuals screened who were found to be ineligible or not interested in participating). For enrolled participants, confidentiality will be maintained by assigning every participant a study ID number (no identifiers) and numerically coding all data. The association of the ID-code and the participant will be kept by the research coordinator in a locked file cabinet at all times. All data obtained through interviews and other subject records will be kept in locked filing cabinets in offices that are kept locked when unoccupied. Subject files will be kept in a secure area, with access only by designated staff members (PI and research coordinator). Any computer storage of data will be password protected and only available to the PIs and the study coordinator.

All information connecting study ID numbers to participant names will be destroyed after completion of the project. Five years after publication of the results (per standard journal guidelines), all paper copies of interview forms, Facebook transcripts and the data base sent to Mayo Clinic for analysis, will be destroyed. Only summaries of group data will be reported in any publications or presentations, with no identification of individuals or villages.

All data elements and data transfer activities will be strictly compliant with HIPAA privacy regulatory requirements. Saliva samples will be shipped directly to Mayo Clinic for analysis of cotinine. These will be labeled with a subject ID number only. Once the specimen sample is processed and results posted, the sample will be destroyed immediately. Interview forms and audio tapes will be labeled with subject ID numbers only; all personal identifiers will be removed before the data are sent to Mayo Clinic for analysis. Standard security measures to store data are in place within the Mayo Clinic. Moreover, at Mayo Clinic the audio tapes will be stored in a locked file drawer accessible only to the PI, [name], and the research assistant, [name].

### **Collection and Reporting of AEs and SAEs**

We will use the FDA definition of adverse events (AEs) and serious adverse events (SAEs). The FDA guidelines for anticipated or unanticipated SAEs will be followed. Regarding monitoring participant safety, anSAE, whether or not it is related to the study intervention, will be reported to the Mayo Clinic IRB, the Alaska Area IRB, and NIDA. The project coordinator and FB intervention moderator both located in Alaska, and the research assistant located at Mayo Clinic, will evaluate for the presence of both SAEs and AEs at each scheduled contact, regardless of whether conducted in person, via telephone, or online. Drs. [name] and/or [name] and will meet with the research staff via teleconference on a bi-weekly basis to review any new or continuing SAEs and AEs.

### **Management of SAEs or Other Study Risks**

A plan is in place for clinical management of depression and other psychiatric symptoms or medical problems. The study staff will refer participants to the appropriate on-call physician or behavioral health clinician at the appropriate Alaska medical facility. The study staff will have a list of contacts as patient issues or concerns arise that are in need of medical or psychiatric attention, or when other types of

referral or assistance are needed. Individuals who report suicidal intent or other severe psychiatric symptoms or medical problems will be referred for treatment and followed throughout the study period. Continued participation with the study will be voluntary and in cooperation with the health care professional treating the subject's psychiatric or medical condition.

The study staff will be trained by Drs. [name] and [name], licensed clinical psychologists, to observe and monitor depression and psychiatric symptoms. They will be available to consult with the study staff as needed.

If the SAE involves death or a life-threatening event, the PI, [name], will be notified immediately by the study staff. [name] will telephone, fax, and/or e-mail the Mayo Clinic IRB chair/vice-chair, Chair of the Alaska Area IRB, and the NIDA Program Official within 24 hours of when she learns of the event. This telephone contact will be followed up with a standardized report form submitted to both the respective IRBs and NIDA within 2 working days of the study staff learning of the SAE. If the SAE involves something other than death or a life-threatening event, [name] will submit a standardized, detailed report of the event to the respective IRBs and NIDA within 2 working days of when the SAE was reported. Reports of serious adverse events received by the respective IRBs will be reviewed by an institutional SAE Board, (the members of these boards are not involved in this study) to make a determination of the seriousness of the event and to determine what actions, if any, will be required. If the SAE Board determines that suspension or termination of the study is required, this information will also be reported to NIDA within 24 hours.

In the event that a participant withdraws from the study or the PI decides to discontinue a participant due to an SAE, the participant will be monitored by the PI via ongoing status assessment until:

- (1) resolution is reached (i.e., the problem requiring treatment has resolved or stabilized with no further changes expected)
- (2) the SAE is determined to be clearly unrelated to the study intervention
- (3) the SAE results in death.

Outcome of SAEs will be reported biannually to NIDA or as otherwise specified by the NIDA Program Official. A summary of the SAEs that occurred during the previous year will be included in the annual progress report to NIDA and to the respective IRBs. All protocol changes and/or protocol amendments will be reported to NIDA, then the IRB. Additionally, a summary of all AEs will be reported in an annual progress report to the respective IRBs.

A determination of the association of the adverse event with the study intervention will be made and appropriate modifications to the protocol will be made if an association is suspected. If protocol modifications to ensure the safety of future study subjects cannot be made, the study will be terminated.

## **TRIAL EFFICACY**

### **Plans for Interim Analysis**

As part of the ongoing data management and statistical activities conducted by the study biostatistician, [name], the study groups will be reviewed on a quarterly basis to assess differential occurrence of the type and number of SAEs and AEs. If any significant difference is found, the relevant covariates will be thoroughly examined in order to understand more completely the relationship between the variables of interest and potential impact of the intervention on SAEs and AEs. The results of our analyses will be reported to both the respective IRBs and NIDA.

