## Formative Work to Develop the Intervention: Aim 1 (Phases 1-3)

### Projected Content and Structure for the Facebook Intervention

Structure and duration. The intervention will consist of a Facebook group moderated by an AN facilitator. To address potential concerns about Facebook privacy, we will utilize a closed and secret Facebook group and a group policy/guideline that emphasizes confidentiality of all content. A secret group is defined as invitation only, with the group and content not visible to anyone on Facebook except participants. Thus, anyone searching on Facebook would not find the group nor be able to request to join. Also, group membership or postings through newsfeeds will not be visible on the participants' personal Facebook page.

We chose to use a moderated group based on research indicating that moderators play a critical role in directing and tailoring content to the group and enhancing overall social media engagement. Also, the frequency of moderator Facebook postings is associated with increased participant engagement.

The Facebook group will be active for 3 months. A content library of moderator postings will be developed for posting within the Facebook group for the 3 months that the group is active. The moderator will check-in with the group about 3-4 times daily to respond to comments and other user-generated content, and to prompt and direct discussions by encouraging participants to share stories about their tobacco use journey. Participants will be notified through news feeds when there is new Facebook content posted.

Content for moderator postings. Moderator postings will be developed from two existing sources.

First are the CDC Tips™ campaign digital story videos. The 31 stories are based on factual appeals to quit smoking and each is about 2.5 minutes long. The stories address different phases of the quitting process, specifically: motivation (why to quit), engaging in treatment (how to quit), and relapse prevention. We anticipate creating about 8-10 new digital stories featuring AN persons. However, based on formative work, we recognize that existing Tips™ stories such as Michael's story (AN former smoker) may be acceptable, and will be included. The digital stories will be embedded in moderator postings as YouTube links.

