**Table 2: Design Elements of Study Groups**

Intervention Components	Intervention Condition Facebook Group + Quitline/Treatment Referral	Control Condition Quitline/Treatment Referral Only
Quitline/treatment referral (both groups)	Description of tobacco treatment services, phone numbers and web links sent via postal mail (printed materials) and email. Treatment options provide free, professional assistance based on U.S. clinical practice guidelines: (1) AK quitline, (2) regional tribal tobacco cessation programs, and (3) smokefree.gov resources (e.g., free texting program and smartphone application, quit guide)	
Facebook Intervention (developed in formative work)	
 
• Participants join a secret (private), culturally relevant Facebook group for 3 months, and moderated by an AN tobacco research counselor
 
• 3 months of moderator postings; plus 3-4 daily check-ins/postings to respond to participant generated content and encourage sharing of personal stories/experiences relevant to all stages of the quitting process and treatment engagement
 
	
 
• No additional intervention provided by research staff
 

[figure not shown]

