### **Frequency of DSM Board**

Every two weeks, the PI [name], Alaska site PI [name], [name] (study statistician), [name](project coordinator), [name] (FB group moderator) and [name] (research assistant) will review the following information in detail at a study-specific meeting via teleconference:

- (1) Subject accrual rate, retention and the reasons for retention failure
- (2) Subject compliance with the protocol
- (3) Project coordinator questions or concerns
- (4) Adherence to FB protocol for moderator postings and adverse events (AEs/SAEs) and other issues reported by participants or the moderator or documented by the research assistant on FB transcripts.
- (5) Adverse events (AEs/SAEs) and other issues reported by participants as documented by the project coordinator on study forms.

Decisions concerning changes, modifications, or adaptations will be decided and acted upon immediately. Annual Reviews: Protocols must be reviewed annually by the Mayo Foundation IRB and the Alaska Area

IRB. Reports will be generated regarding the study progress.

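### The quarterly between-arm adverse event comparison ignores how events were found, although moderator- and transcript-found events can arise only in the Facebook arm

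*Combined protocol and SAP*

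**What the plan says.** Under Trial Efficacy, Plans for Interim Analysis, "the study groups will be reviewed on a quarterly basis to assess differential occurrence of the type and number of SAEs and AEs". If a significant difference appears, covariates that are not named are examined, and the results go to both IRBs and NIDA. The section does not mention how an event came to be known.

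The routes by which an AE can be found are described elsewhere:

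- **Both arms.** The two potential-risks sections (Protection of Human Subjects and Trial Safety) assess adverse symptoms in all pilot participants at the online assessments. The Informed Consent Process invites participants to phone with problems. Frequency of DSM Board, item 5, reviews "issues reported by participants as documented by the project coordinator on study forms".
- **Facebook arm only.** Item 4 of the same list reviews "issues reported by participants or the moderator or documented by the research assistant on FB transcripts". The intervention runs for 3 months, and its description adds: "The moderator will check-in with the group about 3-4 times daily to respond to comments and other user-generated content". For control, Table 2 reads "No additional intervention provided by research staff".
- **Who looks.** Collection and Reporting of AEs and SAEs names the project coordinator, the Facebook moderator and the research assistant. They "will evaluate for the presence of both SAEs and AEs at each scheduled contact, regardless of whether conducted in person, via telephone, or online". Whether a group check-in is a scheduled contact is not stated.

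On reporting, Management of SAEs or Other Study Risks says "a summary of all AEs will be reported in an annual progress report to the respective IRBs", again with no limit by source. It also says "A determination of the association of the adverse event with the study intervention will be made". Content of DSM Report lists AEs and SAEs without a breakdown.

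**The concern.** A between-arm comparison of AE counts is informative about risk when the arms are observed alike. Here one arm has an extra way for events to surface. The expected symptoms of quitting (irritability, anxiety, hunger and so on) are the kind of thing a participant might mention in a group that encourages talk about quitting. A control participant with the same symptom is recorded only by answering a survey or contacting staff.

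If Facebook-found AEs enter the quarterly count, the design pushes the comparison towards more AEs in the Facebook arm even when true risk is equal. Examining covariates cannot remove this, because the route does not exist in control. At stake is the reading of the AE table by the IRBs and NIDA, who could not tell more detection from more harm if sources are not shown.

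**Working it through.** **1. What can be reproduced.** The plan states no AE rate, threshold, significance level or power for this comparison, so there is no figure to reproduce. Arm size is consistent: 30 + 30 = 60 (Sample Size Calculation).

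**2. Routes side by side.**

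| Route | Facebook | Control |
|---|---|---|
| 1-, 3-, 6-month assessments | yes | yes |
| Participant reports to coordinator | yes | yes |
| Participant messages to moderator | yes | none described |
| Found by moderator or on transcripts | yes | none described |

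That the moderator has no contact with control participants is inferred from Table 2 and the Interventions text.

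**3. Illustration at equal true risk.** From the documents: n = 30 per arm, with the group active for 3 of the 6 months. Assumed: six-month AE risk p = 0.40, half of it in the active months; shared routes find a fraction d of AEs; the Facebook route finds a fraction e of the rest.

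- Active-month ratio = [1 − (1 − d)(1 − e)] / d
- Six-month ratio = (active-month ratio + 1) / 2
- Extra participants with an AE = 30 × p × 0.5 × (1 − d) × e

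| d | e | Active-month ratio | Six-month ratio | Extra of 30 |
|---|---|---|---|---|
| 0.7 | 0.3 | 1.13 | 1.06 | 0.54 |
| 0.7 | 0.5 | 1.21 | 1.11 | 0.90 |
| 0.5 | 0.3 | 1.30 | 1.15 | 0.90 |
| 0.5 | 0.5 | 1.50 | 1.25 | 1.50 |
| 0.9 | 0.3 | 1.03 | 1.02 | 0.18 |
| 0.9 | 0.5 | 1.06 | 1.03 | 0.30 |

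Example: 30 × 0.4 × 0.5 × 0.5 × 0.5 = 1.50. For p from 0.2 to 0.6 with d = 0.5-0.7, the extra is 0.27 to 2.25. At an early look with 15 per arm and p = 0.4, it is 0.27 to 0.75. If Facebook-found AEs are not counted, the ratio is 1.0.

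**4. Chance of a nominally significant difference.** Control rate = p × d. Facebook rate = p × [d + 0.5(1 − d)e]. Exact binomial enumeration, n = 30, p = 0.4, Fisher's test at an assumed two-sided 0.05, one look:

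| d | e = 0 | e = 0.3 | e = 0.5 |
|---|---|---|---|
| 0.5 | 2.2% | 2.9% | 3.9% |
| 0.7 | 2.6% | 2.8% | 3.1% |

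The part with the Facebook arm higher rises from 1.1% to 2.3% and 3.6% (d = 0.5), and from 1.3% to 1.9% and 2.4% (d = 0.7). At the far corner of the range (p = 0.6, d = e = 0.5; 37.5% against 30%), total rejection is 5.5%.

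**5. Precision of a shared-assessment comparison.** 95% half-width = 1.96 × √[2q(1 − q)/30], treating the shared-route rate as q. For q = 0.4 × 0.5 = 0.20 it is 20 percentage points; for q = 0.4 × 0.7 = 0.28 it is 23 points. The detection effect at p = 0.4 and d = 0.5-0.7 is 0.54/30 to 1.50/30, or 1.8 to 5 points.

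**The case against.** - **The sources are already kept apart.** The two-weekly meeting lists the Facebook and study-form routes as separate items, and the study statistician attends. Each AE is also assessed for association with the intervention. This stands in part: the team could largely tell the sources apart. But that meeting is not a comparison by arm, the split is not carried into the quarterly comparison, and an event-level judgement does not change the arm counts.
- **The premise is conditional.** No passage says that Facebook-found AEs enter the quarterly count. This stands. The plan neither excludes them nor says that they are included.
- **The consequence is small.** This stands. The planned response to a difference is an examination of covariates and a report; AEs are not among the Endpoints; SAEs should be less affected, being harder to miss; and at the 40% risk used above the test stays below its nominal level.
- **An added comparison cannot separate detection from harm.** This stands at 30 per arm: a half-width of 20 points or more dwarfs an effect of 1.8 to 5. The row makes the table readable; it does not settle the cause.
- **Coordinator reports are not like for like.** This stands. The potential-risks sections let Facebook participants take a problem to the moderator instead. Coordinator reports may therefore be under-counted in that arm, a bias the other way. Only the scheduled assessments are a common route.
- **A source field is procedures-manual detail.** Fair for the form itself, but how the between-arm comparison is presented belongs in the plan.

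A reader might infer that false safety signals become likely. Assume a 20% shared-route rate and a Facebook route that independently adds an AE in a further 10%, 20% or 30% of that arm. The rates are then 28%, 36% and 44% against 20%, and Fisher's test rejects in 6.5%, 20% and 41% of single looks. The documents give no basis for detection gains of that size, so these figures show only that the result follows the assumption.

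**Conclusion.** The point holds as a minor one. The asymmetry in detection is in the text, and the quarterly comparison takes no account of it. If Facebook-found AEs are counted, the direction is towards an apparent excess in the Facebook arm. The size cannot be derived from the documents. At an assumed 40% risk with 50-70% shared detection and 30-50% Facebook detection of the rest, it is about 0.5 to 1.5 participants of 30. It shrinks to 0.2-0.3 if shared routes find 90%, and to nothing if these AEs are not counted. What is affected is the interpretation of the AE table.

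Two stronger readings are not supported. One is that the plan definitely counts these events; it only leaves room for that. The other is that Facebook-found events should be set aside, or an excess discounted until the shared routes confirm it. The plan itself foresees that postings may cause emotional discomfort. AEs caused by the group are real effects, and they would tend to surface through the Facebook-only route.

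**What to change.** 1. Record the detection source of each AE on the AE form, following the split already made in Frequency of DSM Board.
2. Keep the all-source AE and SAE comparison in Plans for Interim Analysis unchanged, and state whether Facebook-found AEs are in it.
3. Beside it, add one between-arm comparison limited to AEs found at the 1-, 3- and 6-month assessments, as a risk difference with confidence interval and with assessment completion by arm. Note that at 30 per arm the half-width is about 20 percentage points or more at the rates illustrated.
4. List participant-initiated reports (to the coordinator or the moderator) and moderator- or transcript-found AEs by arm, descriptively and with no between-arm test.
5. Do not add a rule that an all-source excess must be confirmed on the shared assessments before it is attributed to the intervention.

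The cost is one form field and a few table rows. The shared-assessment row depends on survey completion, which is why completion must be shown. No event leaves the all-source comparison or safety reporting.
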